5.2 Exclusion Criteria

1. Known history of hypersensitivity to or positive serum human ADA to a CD19 antibody
2. Previous therapy with any checkpoint inhibitor
3. Autologous stem cell transplant within 100 days prior to start of study drug (C1D1)
4. History of allogenic stem cell transplant
5. History of solid organ transplant
6. Active or prior documented autoimmune or inflammatory disorders (including inflammatory bowel disease [e.g., colitis or Crohn's disease], diverticulitis [with the exception of diverticulosis], systemic lupus erythematosus, Sarcoidosis syndrome, or Wegener syndrome [granulomatosis with polyangiitis, Graves' disease, rheumatoid arthritis, hypophysitis, uveitis, etc.]). The following are exceptions to this criterion:
 - a. Patients with vitiligo or alopecia
 - b. Patients with hypothyroidism (e.g., following Hashimoto syndrome) stable on hormone replacement
 - c. Any chronic skin condition that does not require systemic therapy
 - d. Patients without active disease in the last 5 years may be included but only after consultation with the Study Physician
 - e. Patients with celiac disease controlled by diet alone
7. Active infection including tuberculosis (clinical evaluation that includes clinical history, physical examination and radiographic findings, and tuberculosis testing in line with local practice)
8. Known seropositive and requiring anti-viral therapy for human immunodeficiency virus (HIV), hepatitis B virus (HBV), or hepatitis C virus (HCV)

9. History of Stevens-Johnson syndrome or toxic epidermal necrolysis
10. Lymphoma with active central nervous system involvement at the time of screening, including leptomeningeal disease
11. Clinically significant third space fluid accumulation (i.e., ascites requiring drainage or pleural effusion that is either requiring drainage or associated with shortness of breath)
12. Breastfeeding or pregnant
13. Significant medical comorbidities, including but not limited to, uncontrolled hypertension (blood pressure [BP] $\geq 160/100$ mmHg repeatedly), unstable angina, congestive heart failure (greater than New York Heart Association class II), electrocardiographic evidence of acute ischemia, coronary angioplasty or myocardial infarction within 6 months prior to screening, uncontrolled atrial or ventricular cardiac arrhythmia, poorly controlled diabetes, or severe chronic pulmonary disease
14. Radiotherapy, chemotherapy, or other anti-neoplastic therapy within 14 days prior to start of study drug (C1D1), except shorter if approved by the Sponsor
15. Major surgery within 28 days prior to start of study drug (C1D1), except shorter if approved by the Sponsor. Note: Local surgery of isolated lesions for palliative intent is acceptable
16. Use of any other experimental medication within 14 days prior to start of study drug (C1D1)
17. Planned live vaccine administration after starting study drug (C1D1)
18. Failure to recover to Grade ≤ 1 (Common Terminology Criteria for Adverse Events [CTCAE] version 4.0) from acute non-hematologic toxicity (Grade ≤ 2 neuropathy or alopecia) due to previous therapy prior to screening
19. Congenital long QT syndrome or a corrected QTcF interval of >470 ms at screening (unless secondary to pacemaker or bundle branch block)
20. History of another primary malignancy except for:
 - a. Malignancy treated with curative intent and with no known active disease ≥ 5 years before the first dose of investigational product and of low potential risk for recurrence
 - b. Adequately treated non-melanoma skin cancer or lentigo maligna without evidence of disease
 - c. Adequately treated carcinoma in situ without evidence of disease
21. History of active primary immunodeficiency
22. Any other significant medical illness, abnormality, or condition that would, in the Investigator's judgement, make the patient inappropriate for study participation or put the patient at risk.

5.3 Screen Failures

Patients who signed the ICF but were found not eligible for the study prior to receiving study drugs are defined as screening failures.

For these patients, only limited information will be collected in the electronic case report form (eCRF):

- Informed consent
- Demographics
- Inclusion/exclusion criteria
- SAE and/or death occurring during the screening period

6 Study Treatment

6.1 Study Drugs

6.1.1 Loncastuximab Tesirine

Loncastuximab tesirine will be provided as a frozen liquid formulation in 10 mL glass vials designed to deliver 3.2 mL of loncastuximab tesirine at a concentration of 5 mg/mL (16 mg loncastuximab tesirine per vial) and stored at -65°C or below. It is a sterile, frozen liquid formulated in 30 mM histidine, 200 mM sorbitol, and 0.02% polysorbate 20, at pH 6.0. Prior to use, the frozen formulation is thawed at ambient temperature, gently swirled to ensure homogeneity, and visually inspected.

6.1.2 Durvalumab

Durvalumab will be supplied as a 500-mg vial solution for infusion after dilution. The solution contains 50 mg/mL durvalumab, 26 mM histidine/histidine hydrochloride, 275 mM trehalose dihydrate, and 0.02% weight/volume (w/v) polysorbate 80; it has a pH of 6.0. The nominal fill volume is 10.0 mL. Durvalumab vials are stored at 2°C to 8°C (36°F to 46°F) and must not be frozen. Drug product should be kept in secondary packaging until use to prevent excessive light exposure.

6.2 Management of Clinical Supplies

Detailed instructions regarding shipment of study drugs, handling, storage, and preparation are included in the pharmacy manual.

6.2.1 Packaging and Storage

The study drugs will be supplied by the Sponsor through the designated distribution center.

Once the package arrives at the study site, the receiving site pharmacy will complete the procedures listed in the pharmacy manual to acknowledge receipt.

All study drugs must be stored in a secure area.

- Loncastuximab tesirine liquid formulation: loncastuximab tesirine should be protected from light and stored frozen (-65°C or below). Loncastuximab tesirine should be thawed under ambient conditions.
- Unopened vials of durvalumab must be stored at 2°C to 8°C (36°F to 46°F) and must not be frozen.

6.2.2 Preparation and Administration

Loncastuximab tesirine solution at the concentration of 5 mg/mL will be the basis for the preparation of the infusion solution. The amount of loncastuximab tesirine to be administered will depend on the dose level and the weight of the patient. Loncastuximab tesirine will be administered as a 30 minute IV infusion. Variations in infusion times due to minor differences in IV bag overfill/underfill and the institution's procedure for flushing chemotherapy lines will not result in protocol deviation.

Durvalumab will be given as a fixed dose of 1500 mg administered as a 60 minute IV infusion. Variations in infusion times due to minor differences in IV bag overfill/underfill and the institution's procedure for flushing chemotherapy lines will not result in protocol deviation.

6.2.3 Accountability

The Investigator must maintain accurate records of receipt of all study drugs, including dates of receipt. In addition, accurate records must be kept regarding when and how much study drugs are dispensed and used by each patient in the study. Reasons for departure from the expected dispensing regimen must also be recorded. All study drugs must be reconciled and retained or destroyed according to applicable regulations.

6.3 Dosing of Study Drugs

6.3.1 Loncastuximab Tesirine Dosing

Administration of loncastuximab tesirine will be performed by the Investigator or a qualified designee.

During Part 1, loncastuximab tesirine will be administered on Day 1 of Cycle 1 and Cycle 2 per the dose escalation plan as shown below.

Loncastuximab tesirine will be given initially for 2 doses, 3 weeks apart.

Loncastuximab Tesirine Dose Escalation

| Dose Level | Loncastuximab tesirine | Durvalumab |
|------------|-------------------------------|----------------|
| 1 | 90 µg/kg IV on Day 1 Q3W × 2 | 1500 mg IV Q4W |
| 2 | 120 µg/kg IV on Day 1 Q3W × 2 | 1500 mg IV Q4W |
| 3 | 150 µg/kg IV on Day 1 Q3W × 2 | 1500 mg IV Q4W |

Patients who have a response of PR or SD at the 15 week assessment may receive two additional doses of loncastuximab tesirine given 4 weeks apart.

Patients with a body mass index (BMI) ≥ 35 kg/m² will have their loncastuximab tesirine dose calculated based on an adjusted body weight as follows:

- Adjusted body weight (ABW) in kg = $35 \text{ kg/m}^2 * (\text{height in meters})^2$
- Dose to administer (mg) = dosage ($\mu\text{g/kg}$) * ABW/1000

During Part 2, patients will receive loncastuximab tesirine on Day 1 of Cycle 1 and Cycle 2 at the recommended dose determined in Part 1. Patients who have a response of PR or SD at the 15 week assessment may receive 2 additional doses of loncastuximab tesirine given 4 weeks apart.

Refer to [Section 6.7](#) for premedication and supportive care.

6.3.2 Durvalumab Dosing

Administration of durvalumab will be performed by the Investigator or a qualified designee.

Durvalumab will be administered at a fixed dose of 1500 mg every 4 weeks. Durvalumab will be administered on Day 8 of Cycle 1, Day 15 of Cycle 2, and Day 1 of subsequent cycles.

6.4 Dose Escalation

6.4.1 Dose Escalation Design

The dose escalation of loncastuximab tesirine in Part 1 will follow a standard 3+3 design using the dose levels defined in [Section 6.3.1](#). Cohorts of 3 patients will be treated, starting at the initial dose level. If 0 of 3 patients in the first cohort at any dose level experience a DLT, then the following cohort will be treated at the next higher dose level. If 2 of 3 patients experience a DLT, then the preceding dose level will be determined as the MTD. If 1 of 3 patients experience a DLT, then 3 additional patients will be treated at that dose level. If 0 of 3 additional patients experience a DLT, then the following cohort will be treated at the next higher dose level. If 1 or more of 3 additional patients experience a DLT, then the preceding dose level will be determined as the MTD.

Patients in Part 1 without a DLT who discontinue from the study prior to completion of the DLT period will be replaced.

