2.1 Rationale for Study Design

As loncastuximab tesirine and durvalumab represent a novel combination, the study will have dose finding using a standard 3+3 dose escalation design, followed by a dose expansion. As toxicity seemed similar across histologies in the Phase 1 study of loncastuximab tesirine, the dose escalation will enroll all histologies. To ensure adequate number of patients for the less common histologies of MCL and FL, the dose expansion will have individual cohorts for each histology.

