9.1 Sample Size

The study will enroll approximately 75 patients. Part 1 (dose escalation) will enroll approximately 15 patients and Part 2 (dose expansion) will enroll approximately 60 patients (20 patients per cohort for up to 3 expansion cohorts, one for DLBCL, one for MCL and one for FL).

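### Section 6.4.1 sets no minimum number of DLT-evaluable patients at the level named as MTD and no end point for level 3, so the named dose would usually rest on 0/3

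*Protocol*

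**What the plan says.** Protocol Section 2.1 describes "dose finding using a standard 3+3 dose escalation design, followed by a dose expansion". Section 6.4.1 gives the rule, and Section 6.3.1 lists three dose levels.

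- Start: "Cohorts of 3 patients will be treated, starting at the initial dose level".
- No DLT in the first three: "If 0 of 3 patients in the first cohort at any dose level experience a DLT, then the following cohort will be treated" one level up. The cleared level keeps 3 patients.
- One DLT in the first three: three more are treated. "If 0 of 3 additional patients experience a DLT, then the following cohort will be treated at the next higher dose level". The cleared level then has 1/6.
- Failure in the first cohort: "If 2 of 3 patients experience a DLT, then the preceding dose level will be determined as the MTD".
- Failure in the second cohort: "If 1 or more of 3 additional patients experience a DLT, then the preceding dose level will be determined as the MTD".

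No step returns to the preceding level to treat more patients. After level 3 is cleared, the text points to a higher level that Section 6.3.1 does not contain, so it states neither an MTD nor a stopping point.

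Section 6.4.4 makes the DESC responsible for dose levels and the MTD, on the basis of safety findings and DLTs, without a minimum number. Section 9.1 sizes the study: "Part 1 (dose escalation) will enroll approximately 15 patients and Part 2 (dose expansion) will enroll approximately 60 patients". Section 4.1 treats Part 2 at the dose that Part 1 determines.

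SAP Section 3.3 reports early termination and restricts the analysis to Part 1. SAP Section 2.1 keeps identification of the recommended dose as an objective, Section 4.1.2 defines the DLT-evaluable set, and Section 4.8.1 lists DLT data without a summary.

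**The concern.** Identifying the recommended dose is part of the primary objective. Under the rule as written, a level passed on 0/3 becomes the MTD as soon as the next level fails, and nobody looks at it again. Three patients without a DLT are compatible with a wide range of DLT rates, including rates well above one third. The protocol itself calls the combination novel.

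Two things are at stake: how much evidence stands behind the dose meant for Part 2, and how a reader of the final report will take the term MTD if it is attached to a level seen in only three evaluable patients.

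**Working it through.** **Inputs.** From the protocol: cohorts of 3, three levels, the rules above, about 15 patients in Part 1 and about 60 in Part 2. The documents give no DLT rates, so all rates below are assumptions.

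**The plan's own figure.** 15 + 3 × 20 = 75, as stated. No derivation is given for the 15. If all three levels are opened at 3 to 6 evaluable patients each, Part 1 uses 9 to 18.

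**Step 1: share of cleared levels resting on 0/3.** With true DLT rate p, a level is cleared

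- on 0/3 with probability (1-p)^3;
- on 1/6 with probability 3p(1-p)^2 × (1-p)^3.

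The share on 0/3 is therefore 1 / [1 + 3p(1-p)^2]. It does not depend on what happens at the next level.

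| p | 5% | 10% | 20% | 30% | 1/3 | 40% | 50% |
|---|---|---|---|---|---|---|---|
| Share on 0/3 | 88.1% | 80.5% | 72.2% | 69.4% | 69.2% | 69.8% | 72.7% |

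The minimum is at p = 1/3: 3 × (1/3) × (2/3)^2 = 4/9, and 1/(1 + 4/9) = 9/13 = 69.2%. The word usually in the heading thus needs no assumed profile.

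**Step 2: what the data exclude.** Exact one-sided 95% upper limits for the DLT rate:

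- 0/3: 1 - 0.05^(1/3) = 63.2%
- 0/6: 1 - 0.05^(1/6) = 39.3%
- 1/6: 58.2% (Clopper-Pearson)

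**Step 3: what a second cohort would catch.** A level passed on 0/3 would show at least 2 DLTs in three further patients with probability 3p^2(1-p) + p^3. This is 10.4% at p = 20%, 21.6% at 30%, 25.9% at 1/3, 35.2% at 40% and 50% at 50%.

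**Step 4: operating characteristics.** All paths through three levels were enumerated exactly, first as written (a cleared level 3 is taken forward), then with confirmation. Under confirmation, if the level to be named has only 3 patients, 3 more are treated. The level is named if at most 1 of 6 has a DLT; otherwise the same test applies one level down. Counts are evaluable patients, without replacements. Arrows run from as written to confirmed.

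| Assumed DLT rates, levels 1/2/3 | Doses carried forward on 3 patients, as written | Mean N | P(N > 15) | Carries forward a true rate of 33% or more |
|---|---|---|---|---|
| 5/10/20% | 75.9% | 10.7 → 13.0 | 0.8% → 4.3% | no such level |
| 10/20/33% | 73.7% | 10.3 → 12.5 | 1.6% → 7.6% | 27.9% → 23.0% |
| 10/25/40% | 74.3% | 9.9 → 12.1 | 1.4% → 7.1% | 16.8% → 12.7% |
| 10/30/50% | 75.3% | 9.5 → 11.7 | 1.0% → 5.8% | 7.7% → 4.9% |
| 20/35/50% | 71.3% | 8.4 → 10.0 | 0.9% → 4.9% | 28.1% → 23.2% |

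The maximum is 3 × 6 = 18 under both rules.

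**Step 5: the matching loss.** For 5/10/20%, where a level 3 rate of 20% would be acceptable, selection of level 3 falls from 62.5% to 57.8%. For 20/35/50%, the chance that no level goes forward rises from 29.1% to 32.7%.

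**The case against.** The other side has several good points.

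- **The gain is modest and has a price.** It is 3 to 5 points, offset by a loss of similar size in selecting an acceptable top level. The confirmed rule still accepts 1/6, whose upper limit is 58%. This stands: a design with at most six patients per level stays imprecise.
- **The sample size margin is thinner than the means suggest.** Section 9.1 counts enrolled patients, and Section 6.4.1 replaces those who leave the DLT period early without a DLT. If 15% were non-evaluable (an assumption), a mean of 13.0 evaluable becomes 13.0/0.85 = 15.3 enrolled. This stands for the most favourable profile; the others leave more room.
- **The DESC can ask for more.** It can, and it weighs all safety findings, not only DLT counts. But no passage obliges it to add patients, and Section 6.4.1 words the MTD step as automatic.
- **There is prior evidence.** Level 3 equals the monotherapy recommended dose, from a study in which 3 of 144 treated patients had a DLT (Section 1.2.2). That bears on the single agent across its own dose range. It informs the combination but does not replace observation of it.

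Stronger readings are tempting but unsupported. A reader might infer that about 60 expansion patients are being exposed on the strength of 0/3; SAP Section 3.3 rules that out, since the trial ended early and only Part 1 is analysed. A reader might infer that the named dose always rests on 0/3; in up to 31% of cleared levels it rests on 1/6. A reader might infer that 3 of 3 DLTs would permit escalation because the rule says 2 of 3; that is a wording slip, not a real path. And nothing here shows that any particular dose is wrong.

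**Conclusion.** The point holds as one of design and reporting. Section 6.4.1 requires no minimum number of evaluable patients at the level it names and does not say how level 3 ends. The 69% floor and the upper limits of 63%, 39% and 58% follow from the rule and the binomial distribution alone, with patients treated as independent. The sample size and selection figures rest on assumed DLT profiles from 5/10/20% to 20/35/50% and on no replacements. Within those, confirmation at six raises mean Part 1 size by about 1.7 to 2.4 patients and stays below the planned 15 on average, while P(N > 15) rises from about 1-2% to 4-8%.

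It is an inexpensive improvement in the evidence behind the primary-objective dose, with error rates traded rather than removed. Early termination takes away the expansion exposure. What remains live is how any recommended dose is described.

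**What to change.** **Still applicable, in the SAP and the report.** For any recommended dose or MTD, state the number of DLT-evaluable patients and DLTs at that level. Where only 3 patients support it, do not call it an established MTD; say that it is a level tested with 0/3 DLTs. SAP Section 4 already sorts listings by dose level and patient, so this needs one sentence or a small table beside the DLT listing in Section 4.8.1, and no new data.

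**For the protocol rule, or any reuse of the design.** Have Section 6.4.1 state that a level, including the top one, is declared the MTD or recommended dose only after 6 DLT-evaluable patients there with at most 1 DLT. Let the DESC text in Section 6.4.4 refer to that condition. Correct the first-cohort wording to 2 or more of 3 at the same time. The cost is an amendment, usually 3 more patients, and the loss in top-level selection shown above. This concerns the evidence required behind a named dose; it does not say which dose is right.

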6.4.2 Dose Limiting Toxicity Period

For patients in Part 1, the DLT period will be the 21 days after the first durvalumab dose. Any treatment-related toxicities that first occurred during the DLT period must be followed for resolution to determine if they qualify as a DLT as specified in the DLT criteria below.

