4.3 Treatment Period

The treatment period starts on the date when a patient receives the first dose of study drug and continues until the End of Treatment (EOT) visit.

The treatment will start with Cycle 1, which will be 3 weeks long (i.e., 21 days), Cycle 2 will be 6 weeks long because durvalumab administration needs to be 4 weeks apart, and all other subsequent cycles will be 4 weeks long. Loncastuximab tesirine will be administered as an intravenous (IV) infusion over 30 minutes on Day 1 of Cycles 1 and 2. All patients will receive loncastuximab tesirine every 3 weeks (Q3W) for 2 cycles. Patients who have a response of PR or stable disease (SD) at the Week 15 assessment may receive an additional 2 doses of loncastuximab tesirine given on day 8 of Cycles 5 and 6.

Durvalumab will be administered as an IV infusion over 60 minutes on Day 8 of Cycle 1 and Day 15 of Cycle 2, then on Day 1 of subsequent cycles.

Patients may continue treatment for up to 1 year or until disease progression, unacceptable toxicity, or other discontinuation criteria ([Section 7](#)), whichever occurs first.

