6.4.3 Dose Limiting Toxicity Definition

A DLT defined as any of the following events, which occur during the 21-day DLT evaluation period of Part 1, except those that are clearly due to underlying disease or extraneous causes:

A **hematologic** DLT is defined as:

- Grade 4 anemia
- Grade 3 anemia requiring transfusion
- Grade 4 neutropenia lasting > 7 days
- Febrile neutropenia
- Grade 4 thrombocytopenia
- Grade 3 thrombocytopenia which results in clinically significant bleeding or requires a transfusion

A **non-hematologic** DLT is defined as:

- Hy's law case - AST and/or ALT $\geq 3 \times$ ULN and bilirubin $\geq 2 \times$ ULN, and without initial findings of cholestasis (serum alkaline phosphatase [ALP] activity $< 2 \times$ ULN) and no other reason that could explain the combination of increased transaminases and serum total bilirubin
- Any other non-hematologic toxicity \geq Grade 3 with the exception of the following:
 - Grade 3 fatigue for ≤ 7 days.
 - Grade 3 nausea, vomiting, or diarrhea in the absence of premedication that responds to therapy and improves by at least 1 grade within 3 days or to \leq Grade 1 within 7 days.
 - Grade 3 elevations of ALP and GGT elevations, unless considered clinically relevant by the Investigator.
 - Grade 3 elevation of serum lipase or serum amylase for ≤ 7 days if without clinical signs or symptoms of pancreatitis.
 - Grade 3 electrolyte abnormalities that normalize within 48 hours (with or without medical intervention) and that do not manifest themselves clinically; in such instance, a follow-up sample MUST be taken within 48 hours to check whether such normalization has occurred.

- In addition, the following will be considered DLTs:
 - Grade 2 noninfectious pneumonitis that does not resolve to \leq Grade 1 within 3 days of the initiation of maximal supportive care
 - Any grade of immune-mediated rash with bullous formation
 - Grade 2 or 3 immune-mediated peripheral neuromotor syndrome (such as Guillain-Barre and myasthenia gravis) that does not resolve to Grade \leq 1 within 30 days or that exhibits signs of respiratory insufficiency or autonomic instability
 - Grade 2 immune-mediated myocarditis that does not resolve to Grade \leq 1 within 3 days of initiating optimal medical management, including systemic corticosteroids

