6.5.2 Durvalumab

If a patient experiences any Grade ≥ 3 toxicity, durvalumab must be held until the toxicity resolves to Grade 1 or less (Grade 1 or baseline for peripheral neuropathy).

In addition, durvalumab must be held for the following Grade ≥ 2 specific immune-mediated toxicities:

- Pneumonitis/ILD
- Diarrhea/Colitis
- Hepatitis (elevated liver function tests)
- Nephritis or renal dysfunction
- Persistent rash (>1 -2 weeks)
- Endocrinopathy (except isolated hypothyroidism or Type 1 diabetes mellitus)
- Neurotoxicity
- Peripheral neuromotor syndromes
- Myocarditis
- Myositis/polymyositis

See [Section 13.3](#), [Appendix 3](#) for guidelines regarding management and resumption of durvalumab therapy after specific immune-mediated toxicities.

For all other toxicities, durvalumab must be held until the toxicity resolves to Grade 1 or less (Grade 1 or baseline for peripheral neuropathy).

Durvalumab will be given at full dose when resumed after being held for toxicity, i.e., there will be no dose reduction.

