4.1.2 DLT-evaluable Analysis Set (Part 1)

The DLT-evaluable analysis set consists of all patients in Part 1 who received study drugs and excludes patients who discontinue from the study during the DLT evaluation period without experiencing a DLT. The patients with completed DLT information will be included even if they discontinue early before the end of DLT evaluation period. The DLT evaluation period will be the 21 days after the first durvalumab dose.

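### Loncastuximab toxicity that meets the DLT criteria before the first durvalumab dose is not counted as a DLT, so the 3+3 count and the DLT endpoint can understate first-week toxicity

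*Protocol*

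**What the plan says.** Protocol 6.4.1 defines what is escalated: "The dose escalation of loncastuximab tesirine in Part 1 will follow a standard 3+3 design". Section 6.3.1 sets the levels at 90, 120 and 150 µg/kg with durvalumab fixed at 1500 mg. On timing, Section 4.3 states: "Loncastuximab tesirine will be administered as an intravenous (IV) infusion over 30 minutes on Day 1 of Cycles 1 and 2". Section 6.3.2 states: "Durvalumab will be administered on Day 8 of Cycle 1, Day 15 of Cycle 2, and Day 1 of subsequent cycles".

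The DLT period is anchored to the second drug: "For patients in Part 1, the DLT period will be the 21 days after the first durvalumab dose" (6.4.2). The synopsis, Table 2, Section 4.1 and SAP 4.1.2 agree. Section 6.4.3 limits DLTs to listed events "which occur during the 21-day DLT evaluation period of Part 1".

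Three further rules bear on a patient with early toxicity:

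- Replacement (6.4.1): "Patients in Part 1 without a DLT who discontinue from the study prior to completion of the DLT period will be replaced". Section 7.2 lists death as a reason for leaving the study.
- Hold (6.5.2): after any toxicity of Grade 3 or higher, "durvalumab must be held until the toxicity resolves to Grade 1 or less".
- Analysis set (SAP 4.1.2, and Protocol 9.2 in nearly the same terms): the set takes Part 1 patients who received the study drugs and "excludes patients who discontinue from the study during the DLT evaluation period without experiencing a DLT".

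SAP 3.3 records early termination, with only Part 1 analysed, and SAP 4.8.1 says that DLT data will be listed. SAP 2.1 keeps identification of a recommended dose as part of the primary objective.

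**The concern.** A 3+3 rule works only on what it counts. Here the count starts a week after the first dose of the drug whose dose is being chosen. The omission has one direction: leaving out qualifying events can only make a dose level look safer.

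The rules also interact. A severe event on Days 1-7 triggers the durvalumab hold, so the DLT period opens late or not at all. If the patient then leaves the study, the replacement rule treats that patient as having had no DLT and recruits another. A fatal loncastuximab toxicity on Day 5 would be handled this way. At stake are the formal escalation count, the primary DLT endpoint, and any dose conclusion drawn from the DLT listing.

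**Working it through.** **Timeline.** Cycle 1 lasts 21 days, so loncastuximab is given on Days 1 and 22. Durvalumab starts on Day 8, and the DLT period ends about Day 8 + 21 = Day 29. It misses the first 7 days after dose 1 and covers about 29 − 22 = 7 days after dose 2. With the ±2-day visit window, durvalumab can fall on Days 6 to 10, so 5 to 9 days are missed.

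**Status of a patient whose event meets the criteria on Days 1-7.**

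| What happens next | Result under the text |
|---|---|
| Leaves the study, or dies | No DLT; replaced (6.4.1) |
| Stops treatment, stays in follow-up | Not replaced: 7.1 says that stopping treatment is not automatically withdrawal. The DLT period never opens, and the exclusion in Protocol 9.2 and SAP 4.1.2 covers only departures during that period. Whether receiving the study drugs means both drugs is not stated |
| Recovers, then receives durvalumab | Period opens, possibly late; the early event is not a DLT |

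A toxicity that begins before Day 8 and reaches a DLT grade after it is a separate ambiguity. Section 6.4.2 turns on first onset within the period, while 6.4.3 asks only that the event fall within it.

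**Size.** The documents give no operating characteristics for the 3+3 rule, so there is no stated figure to reproduce. The planned enrolment, 15 + 3 × 20 = 75, adds up and is not in dispute.

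Under 6.4.1 a level is passed after 0 of 3 DLTs, or after 1 of 3 followed by 0 of 3. With per-patient DLT probability p and q = 1 − p:

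P(pass) = q³ + 3pq² × q³.

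Let b be the risk of a DLT inside the period and a the risk of a qualifying event on Days 1-7, taken as independent. Both are assumptions. As written, with early cases replaced, p = b. If Days 1-7 counted, p = 1 − (1 − a)(1 − b).

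For b = 0.25 as written: q³ = 0.4219 and 3pq² = 0.4219, so P(pass) = 0.4219 + 0.4219 × 0.4219 = 0.600. For b = 0.25 and a = 0.10: p = 1 − 0.90 × 0.75 = 0.325, q³ = 0.3075, 3pq² = 0.4442, so P(pass) = 0.3075 + 0.4442 × 0.3075 = 0.444.

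| b | As written | a = 3% counted | a = 5% counted | a = 10% counted |
|---|---|---|---|---|
| 20% | 0.709 | 0.656 | 0.622 | 0.536 |
| 25% | 0.600 | 0.552 | 0.520 | 0.444 |

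If early cases were instead kept as DLT-free, the visible rate would fall below b. With b = 0.25 and a = 0.10 it is 0.90 × 0.25 = 0.225, and P(pass) = 0.654.

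Among the roughly 15 planned Part 1 patients, the chance of at least one uncounted event is 1 − (1 − a)^15: 54% at a = 5% and 79% at a = 10%. The number actually enrolled is not given.

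**The case against.** The strongest defence is that the window is a deliberate choice, stated consistently. The objective is the safety of the combination. Days 1-7 are loncastuximab alone, at no more than 150 µg/kg, the recommended maximum Phase 2 dose from a single-agent study that treated 144 patients (1.2.2). That context stands, but it does not settle the matter. The same section says that the single-agent MTD was not formally established, and the regimen being recommended includes the Day 1 dose.

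Three further points stand and limit the concern. Loncastuximab toxicity from Day 8 onward, including about a week after dose 2, is captured. The steering committee sets dose levels and the MTD on safety findings as well as DLTs (6.4.4). Early events are collected from consent (8.2.2) and tabulated by dose level as treatment-emergent events, including Grade 3 or higher, serious and fatal ones (SAP 4.8.2). Committee review is discretionary, however, and neither safeguard alters the 3+3 count, the replacement rule or the DLT listing.

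A reader might infer that every severe early event leads to replacement, or that such patients are kept as DLT-free. The documents do not establish either. Replacement needs departure from the study, and a hold only delays durvalumab if the toxicity resolves. SAP 4.1.2 refers to study drugs in the plural, whereas the safety set in SAP 4.1.1 needs any study drug, so a patient given loncastuximab alone may already fall outside the DLT set. The status is unclear rather than wrong in a known direction.

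**Conclusion.** The point holds for a toxicity that both occurs and meets the DLT criteria before first durvalumab: the text leaves it out of the DLT count, and replaces the patient if the patient leaves the study. The count can therefore understate toxicity from the first week after dose 1.

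Its size cannot be derived. The single-agent study reports DLTs in 3 patients without onset days, so neither a nor b has a source. The fall from 60% to between 55% and 44% illustrates sensitivity and is not an estimate.

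It would go too far to conclude that the actual escalation decisions or recommended dose were biased. The documents do not show that any such event occurred, and the committee could have acted on one. Because the trial ended early, the practical consequence now lies mainly in the SAP's DLT set and listing, and in how a dose conclusion is read from them.

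**What to change.** **SAP 4.1.2 and 4.8.1.** List and count, by dose level, all Part 1 events meeting the Protocol 6.4.3 criteria from Cycle 1 Day 1 to 21 days after first durvalumab, flagged as before or after first durvalumab. For toxicities that straddle the first durvalumab dose, show both the onset date and the date on which the criterion was met. Keep a patient with a qualifying pre-durvalumab event in this count as having an event, including a patient who never received durvalumab. List every replaced patient with the reason. Base the interpretation of any dose conclusion on this count.

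**Protocol.** The sponsor should reconcile the DLT period (6.4.2, 6.4.3) with the Day 1 start of the escalated drug, the replacement rule (6.4.1) and the durvalumab hold (6.5.2), so that an early severe event cannot drop out of the escalation count. This cannot change past decisions, but matters if the design is used again.

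**Cost.** Wording, one listing and one count. Hematology and chemistry are already scheduled on Cycle 1 Days 1 and 8, and adverse events are already collected, so no new data are needed. The reported rate of DLT-type events may be somewhat higher, and escalation would be more cautious if the protocol window changed; on the assumptions above, that could range from slight to substantial.
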